6. RECRUITMENT METHODS

- *Describe the source of potential subjects*
- *Describe the methods that will be used to identify potential subjects*
- *Describe any materials that will be used to recruit subjects. A copy of any advertisements (flyers, radio scripts, etc.) should be submitted along with the protocol.*
- *If monetary compensation is to be offered, this should be indicated in the protocol*

Advisory Board and Usability Testing (Aim 1): Advisory board and usability testing recruitment will utilize the assistance of Drs. [name] and [name], who will refer eligible patients and caregivers who express interest in participating in this phase to the CRC/RA. These patients and caregivers will be called by the CRC/RA to reassess interest. If the patient or caregiver are still willing to participate, the CRC/RA will either mail or email the web-based intervention wireframes to participants. The CRC/RA will schedule a mutually agreeable time to speak over the phone to discuss the RSBC intervention. At this time, the CRC/RA will ask participants if they are interested in participating in the usability testing. If the patient and their caregiver are willing to participate, the CRC/RA will schedule a mutually agreeable time to meet for enrollment and usability testing. On the day of the testing, the CRC/RA will approach the patient and their caregiver. If patient and caregiver agree to participate, they will be asked to sign an IRB approved consent forms once the study has been fully explained to them and after they have had an opportunity to ask clarifying questions. They will then be asked to go through the testing process alongside the PI and research staff.

Patients and caregivers will be compensated \$150 in the form of a ClinCard for their participation.

RCT (Aim 2): Patients will be recruited from the Smith Institute for Urology at Northwell Health. CRC/RAs will have access to the EMR of collaborating Northwell Health physicians that perform radical cystectomy and urinary diversion. They will screen these physician's schedules regularly to identify potentially eligible patients. CRC/RAs should confirm with the treating physician that the patient is eligible to be enrolled. Eligible patients will be called by the CRC/RA prior to enrollment to assess interest. If the patient and their caregiver are willing to participate, the CRC/RA will schedule a time to review the study, aiming for 1 week prior to surgery (or at an alternate time that that is convenient for the participant) for enrollment, baseline, and pre-treatment intervention. On the day of their visit, the CRC/RA will approach the patient and their caregiver. If patient and caregiver agree to participate, they will be asked to sign an IRB approved consent forms once the study has been fully explained to them and after they have had an opportunity to ask clarifying questions. If patients and caregivers are not interested in the study, reasons for declining will be recorded, and they will be thanked for talking to the research team. They will then be asked to complete the baseline assessment and the CRC/RA will introduce the study modules of the intervention.

Patients and caregivers will be compensated \$30 in the form of a ClinCard for each completed assessment (Baseline, 1-, 3-, 6-, 12-month). In total, they may receive up to \$150 in compensation.

Hybrid Remote and In-Person Recruitment for RCT: Due to the COVID-19 pandemic, we will utilize a hybrid remote and in-person recruitment process. The study team will ask to meet with subjects in-person at their pre-surgical testing visit at [name] for the Baseline visit (in-person enrollment detailed above). Alternatively, if patients prefer to complete everything remotely online, via phone, or mail, the study team will accommodate this. All recruitment at SIUH will be remote as there are no research assistants onsite. Screening procedures will remain the same as detailed above. However, for remote enrollment, the consent process, administration of intervention materials, baseline and follow-up visits will be conducted via phone, REDCap (email) or mail. Please see section 11, page 13 for more details regarding remote enrollment.

7. ELIGIBILITY CRITERIA

- *Describe the characteristics of the subject population, including their anticipated number, age, ranges, sex, ethnic background, and health status. Identify the criteria for inclusion or exclusion of any subpopulation.*
- *Explain the rationale for the involvement of special classes of subjects, such as fetuses, pregnant women, children, prisoners or other institutionalized individuals, or others who are likely to be vulnerable. You cannot include these populations in your research, unless you indicate such in the protocol*
- *Similarly, detail exclusionary criteria: age limits, special populations (minors, pregnant women, decisionally impaired), use of concomitant medications, subjects with other diseases, severity of illness, etc.*

Advisory Board and Usability Testing (Aim 1): Since this group of patients has already been determined based on a previous IRB approved study below is an overview of the current advisory board that has agreed to participate in this current research study:

- Members of the NWH/MMC AB are diverse with respect to age, race, and BC treatment. Specifically, two-thirds of the board is male, which is consistent with the prevalence of the disease among men. Two members had a neobladder, one a catheterizable pouch and three an ileal conduit. Board members are on average 63 years old and completed treatment an average of two years ago.

RCT (Aim 2):

1) **Patients:** Eligible patients will include men and women who been diagnosed with BC (as confirmed by a biopsy), and scheduled a radical cystectomy. We will include patients diagnosed with any bladder malignancy which includes both muscle invasive bladder cancer (MIBC) and non-muscle invasive bladder cancer (NMIBC) patients, so long as the patient is having a cystectomy with one of the three urinary diversions (i.e., ileal conduit, neobladder or Indiana pouch). 2)

Caregivers: Enrollment will occur for any person who has agreed to a caregiving relationship (e.g., spouse, partner, son, daughter, sister, brother) as stated by both patient and caregiver. **Exclusion Criteria:** Patients and Caregivers will be excluded if they meet one or more of the following criteria: 1) Less than 18 years old or 2) Unable to read and understand English.

Note: Due to the limited number of cystectomies performed at Northwell per year, we will allow patients to enroll in the study if they meet one of the following criteria: 1) Do not have a caregiver, 2) Have a caregiver that does not want to participate, or 3) Caregiver is ineligible for the study for another reason. We will also allow the enrollment of caregivers without the patient if the patient is not eligible or does not want to enroll for similar reasons listed above.

8. NUMBER OF SUBJECTS

- *Indicate the total number of subjects to be accrued locally. If applicable, distinguish between the number of subjects who are expected to be pre-screened, enrolled (consent obtained), randomized and complete the research procedures.*
- *If your study includes different cohorts, include the total number of subjects in each cohort.*
- *If this is multisite study, include total number of subjects across all sites.*

Advisory Board and Usability Testing (Aim 1):
Patient and Caregiver Pairs $n=6$ NWH / $n=6$ FCCC/Temple
12 Pairs Total

RCT (Aim 2):

Total	N=238 (N=287 + 15% attrition) 
 • Patients=153, Caregivers=85
NWH	N=78 (N=97 + 15% attrition)
FFCC	N=141 (N=190 + 15% attrition)

9. STUDY TIMELINES

- *Describe the duration of an individuals participation in the study*
- *Describe the duration anticipated to enroll all study subjects*
- *The estimated date of study completion*

Advisory Board and Usability Testing (Aim 1): The advisory board members will speak over the phone with the study team once in Year 1 for approximately 20 minutes to discuss RSBC intervention. At the end of phone call, CRC/RA will ask participants if they would be interested in the usability testing. Individuals participating in the usability testing will be enrolled into the study for 1 day for approximately 60 minutes per pair.

RCT (Aim 2): An individual's participation in this phase is expected to last for 12 months. To better understand participant satisfaction and use of the RSBC intervention program (CRIS), they may be invited for a brief follow-up interview.

Duration to Enroll: Duration of enrollment is expected to last 2.5 years, from the 1st enrollment of individuals for the advisory board to the final enrollment of individuals for the RCT phase.

Date of Study Completion: We anticipate study completion by December 2024.

10. ENDPOINTS

- *Describe the primary and secondary study endpoints*
- *Describe any primary or secondary safety endpoints*

Primary outcomes for both patients and caregivers will be improved QOL, which is hypothesized to be significantly higher among participants randomized into *Recovery Support for Bladder Cancer* intervention. Secondary outcomes will be fewer infections and nurse-ER visits for patients randomized into the *Recovery Support for Bladder Cancer* intervention.

11. RESEARCH PROCEDURES

- *Include a detailed description of all procedures to be performed on the research subject and the schedule for each procedure.*
- *Include any screening procedures for eligibility and/or baseline diagnostic tests*
- *Include procedures being performed to monitor subjects for safety or minimize risks*
- *Include information about drug washout periods*
- *If drugs or biologics are being administered provide information on dosing and route of administration*
- *Clearly indicate which procedures are only being conducted for research purposes.*
- *If any specimens will be used for this research, explain whether they are being collected specifically for research purposes.*
- *Describe any source records that will be used to collect data about subjects*
- *Indicate the data to be collected, including long term follow-up*

The entire study will first be reviewed by the Institutional Review Boards (IRB) for each site. With the help of the participating physicians, we will inform key staff within NWH, FCCC/TUH and MMC about our study and design. Any concerns will be addressed in advance of initiating recruitment for any phase of the study.

Advisory Board and Usability Testing (Aim 1):

Board members will be contacted to reassess interest in participating and determine phone call meeting time. RSBC intervention wireframes will be sent to participants through his/her preferred method of delivery (mail or email) prior to the scheduled

phone call meeting. During phone call meeting, participants will be asked to provide feedback on the wireframes provided. The phone call will last for approximately 20 minutes and only document participant feedback on the wireframes themselves. Following completion of this phone call the PI and RA/CRC will ask if they would be interested in participating in usability testing.

If the patient and their caregiver are willing to participate, the CRC/RA will schedule a mutually agreeable time to meet for the 1 day of testing. Upon arrival the CRC/RA will explain the study in detail, and participants will have the opportunity to ask clarify questions. If they agree to participate, they will be asked to sign an IRB approved consent and video authorization form. Each usability session will be audio recorded and transcribed and will begin by asking the participant to explore the software on their own, followed by accomplishing specific tasks that are given to them. Participants will be asked to talk aloud while performing these tasks. Lastly, participants will complete the System Usability Survey. Procedures for analyzing the results will be identical to those used for the pre-treatment component. Any issues with content, functionality, and features will be addressed in the second round of development.

RCT (Aim 2):

Recruitment: Patients will be recruited from the Smith Institute for Urology at Northwell Health. CRC/RAs will have access to the EMR of collaborating Northwell Health physicians that perform radical cystectomy and urinary diversion. They will screen these physician's schedules regularly to identify potentially eligible patients. CRC/RAs should confirm with the treating physician that the patient is eligible to be enrolled. Eligible patients will be called by the CRC/RA prior to enrollment to assess interest. If the patient and their caregiver are willing to participate, the CRC/RA will schedule time to meet, aiming for 1 week prior to surgery (or at an alternate time that is convenient for the participant) to conduct the enrollment/ baseline visit.

Hybrid Remote/In-Person Recruitment due to COVID-19 pandemic: In March 2020, in-person recruitment for research was stopped in order to protect patients and research personnel. However, as of March 2021, limited in-person study procedures are allowed. To maintain recruitment efforts, research coordinators will reach out to patients and enroll them in-person at [name], or remotely. The research assistants will ask which method of recruitment the participant is comfortable with. In-person enrollment was detailed previously. For remote enrollment, the consent process can be conducted over the phone. CRCs/RAs will first send the written consent form electronically or by mail, as per the participant's request. The participant will read the consent form and call or email the investigator if he/she wishes to discuss the research and resolve issues/questions. If the participant agrees to participate, they will be directed to sign the consent form and return back to the study team. This can be accomplished electronically (i.e., via the REDCap informed consent form link or scanned copy of consent form sent to the study team) or via mail (i.e., study team provides stamped return envelope for

participants to mail back consent form). Once the ICF is complete, enrollment, randomization, baseline and follow-up procedures will proceed as described below. Regarding the intervention materials, participants in both groups will receive all of their information electronically or by mail (e.g., link to website, username/password, PDFs of the brochures, etc.). Coordinators will also offer to send the Samsung Tablets and Facing Forward brochures via mail.

Enrollment (Baseline Visit): On the day of their enrollment visit, the CRC/RA will approach the patient and their caregiver. Interest in the study will be confirmed for both patients and caregivers and they will be provided with an electronic or physical copy of the consent form according to their preference. The study will be explained in detail, and participants will have the opportunity to ask clarifying questions. If they agree to participate, they will be asked to sign the IRB approved consent form. Following the completion of the consent form the CRC/RA will administer the baseline questionnaire, separately for patients and caregivers. Participants will have the option of completing the baseline questionnaire electronically (i.e., via REDCap link), via hard copy (i.e., mailed form), and over the phone or in-person with the CRC/RA. In the event that participants opt to complete the questionnaire via mailed copy, over the phone or in-person, the CRC/RA will input participant responses into REDCap. All surveys will be created and data housed in REDCap and the CRC/RA will be in charge of maintain the database alongside the assistance of Northwell's REDCap team.

Randomization: All participants who have agreed to participate will be block randomized by study site to either RSBC or the comparison condition. This procedure will ensure that an even number of participants will be allocated to the two conditions and even numbers per condition across sites are maintained overall.

Module 1: The first part of the intervention, Module 1, will consist of the standard of care (SOC) pre-surgery education that all patients undergoing a radical cystectomy receive. Both of the study sites have a robust pre-surgery education that includes information on pre and post treatment care that is conducted by a trained health care provider. Since Module 1 is not conditional upon enrollment in the study and is part of standard of care, it can be performed before informed consent is obtained and/or after Module 2 is administered. The content of Module 1 will be the same for both the intervention and control groups. It is estimated that the entire session will last approximately 50-60 minutes.

Module 2: Following completion of the baseline surveys during the enrollment visit, participants will receive the Module 2 study materials for the group they were randomized to. Subjects randomized to the control group will receive the Facing Forward brochures (either electronically or via mail, according to participants' preferences). Those randomized to the intervention group will be given the link to the intervention website and assigned unique usernames and passwords to access the site. If participants do not have a personal tablet, smartphone, or computer, a tablet with Internet access (Samsung Galaxy Tablet) will be provided. Only 1 tablet

will be provided per dyad. In certain circumstances where the dyad does not live together, and neither party has a personal tablet, smartphone or computer, 2 tablets may be provided. Both participants will be asked to sign a “Study Device: Code of Conduct” agreement which explains that the tablets do not belong to the subject, must be cared for, and must be returned at the end of the study or at the request of the study team. All participants will be thanked and reminded that study personnel will contact them to complete their 1-month follow-up assessment. At the six-month time point, the CRC/RA will contact the participants in the intervention group to schedule a time to return the tablet. At this point, the CRC/RA will also remind patients and caregivers in both study arms to complete their 6-month assessments. Participants will also complete assessments at 12-months. It should be noted that participants will have the option of completing all follow-up assessments electronically (i.e., via REDCap link), via hard copy (i.e., mailed form), and over the phone or in-person with the CRC/RA. In the event that participants opt to complete the questionnaire via mailed copy, over the phone or in-person, the CRC/RA will input participant responses into REDCap.

To better understand participant satisfaction and the use of the RSBC intervention program (CRIS), participants may be invited for a brief follow-up interview, which will be conducted over the phone.

Procedures for obtaining tablets in which participants are not responsive will be to reach out to the physician for the patient and confirm their next appointment during which the physician will remind the patient that the tablet is required to be returned and further this by having the CRC/RA present before or after the appointment to ensure they know who they can reach out to in order to set up a time to have the tablet returned.

12. STATISTICAL ANALYSIS

- *Describe how your data will be used to test the hypotheses.*
- *State clearly what variables will be tested and what statistical tests will be used.*
- *Include sample size calculations.*
- *If this is a pilot study, state which variables will be examined for hypothesis generation in later studies.*

Preliminary analyses. Summary scales of standardized measures will be computed. Univariate and descriptive analysis will be performed on all continuous outcome variables and, if necessary, normalizing and/or variance stabilizing transformations will be sought before the inferential analyses are conducted. We will examine the data for outliers and will use descriptive and inferential statistical techniques for data characterization. First, correlations will be computed, separately for patients and caregivers among background, moderator, mediator, and outcome variables. Any differences between patients and caregivers will be explored with t-tests or ANOVA procedures. Differences among study sites will also be explored and adjusted for in all subsequent analyses. Google analytics (GA) will be applied

to assess program usage, using the following parameters: time/date of login, duration of page views, and document download. These data will be summarized and correlated with study outcomes.

Analyses of the intervention effect. Analyses for patients and caregivers will be conducted separately. A multivariate linear mixed effect model will be used to examine predictors of the primary study outcome QOL after adjusting for other patients/caregivers and clinical characteristics (e.g. comorbidities, study site; [Aim 2](#)). This model will be used because we assume outcomes within each patient/caregivers may be correlated over time and also patients/caregivers outcomes may be correlated within each site.

Moderator analyses ([Aim 3a](#)) with the hypothesized moderators age, gender, and diversion type will be conducted with Proc Mixed in SAS v9.4 to examine whether the intervention works best for patients of older age, caregivers of female gender, and among patients with an ileal conduit diversion type. Specifically, in the linear mixed effect model, we will add separate interaction terms of intervention group and age, gender, and diversion type. Any interaction term that is statistically significant ($p < .05$) will stay in the final model so that the independent effects of the corresponding moderators will be determined. If an interaction term, for incidence, gender, and intervention group is statistically significant, it means gender is a moderator of the causal effect of intervention on QOL (i.e. the effect of intervention on QOL differs between male and female). **Mediating analyses** ([Aim 3b](#)) will explore if higher patient activation and lower levels of distress will mediate the intervention effect. We are following MacKinnon's^{106,107} recommendation to assess either the difference between the direct effect of the intervention in a model with vs. without the mediator, or the product of two path coefficients to examine mediational effects. These approaches are superior to that of Baron and Kenny. The significance of the mediated effect is tested via bootstrapping. First, mediators will be tested separately. If significant mediation effects are found, we will then simultaneously incorporate all significant components in the regression for a multiple mediation model.

Cost analysis. To analyze the costs and potential savings of the intervention over time, we will first assess the overall development, implementation and maintenance costs of the intervention and compare them to the potential savings realized by reduced visiting nurse and ER/Hospital visits. We will conduct a cost-benefit analysis (CBA) between RSBC and comparison groups. To evaluate the cost-effectiveness of RSBC, we will conduct an analysis using QALY and ICER. We will calculate average QALYs for each group and compare ICER between groups.^{106,107,110} We will then perform a stratified analysis for different subgroups (e.g., age groups; diversion type groups) to further understand how cost-effectiveness might differ across subgroups. We will conduct sensitivity analysis and we will examine the cost-effectiveness from the societal cost angle.

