We propose to address these unmet needs through the refinement and evaluation of a comprehensive, 2-part (in-person and web-based) intervention, geared towards the patient and caregiver. Specifically, during Aim 1, the formative phase, we propose to further refine our newly developed intervention components with the help of an established patient/caregiver advisory board. The intervention, Recovery Support for Bladder Cancer (RSBC), consists of a pre-treatment, in-person preparatory instructional session with a trained health care professional (Module 1) to equip patients and caregivers with the skills to adjust to the upcoming treatment and recovery period. This is followed by a post-treatment, interactive web-based program (Module 2) to provide further support for both patients and caregivers to enhance quality of life (QOL) and reduce infections and nurse/ER visits. The RSBC intervention will be evaluated in a 12-month randomized controlled trial (Aim 2) among patients and caregivers (N=287 participants; 238 final sample) against a time and attention comparison condition that incorporates modules focusing on wellness. Primary outcomes for both patients and caregivers will be improved QOL, which is hypothesized to be significantly higher among participants randomized into RSBC. Secondary outcomes will be fewer infections and nurse-ER visits for patients randomized into RSBC. Aim 3 proposes moderator (i.e., age, gender, surgical diversion type) and mediator (i.e., patient activation, distress) analyses of intervention efficacy. We hypothesize that RSBC will be significantly more successful among (a) older, (b) female participants, and (c) patients with a conduit diversion type. Elevated levels of patient activation (i.e., higher self-care knowledge, self-efficacy, lower distress) will mediate the intervention effects. Exploratory Aim 4 will examine the costs and potential savings

associated with developing and implementing the RSBC intervention. We hypothesize that initial development and implementation costs of RSBC will be offset by reduced nurse/ER visits.

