Specific Aim 2: Conduct a rigorous 12-month randomized controlled trial with BC patients and their caregivers at three diverse hospital systems. Patient and caregivers (N=287 participants) will be randomized into the (a) RSBC intervention or (b) time and attention comparison condition that incorporates appropriate health promotion adapted from our prior work (final N= 238 participants). Patients and caregivers in the intervention group compared to the comparison group will experience improved QOL (**primary outcome**) both in the short- (6 mo post-op) and long-term (12 mo post-op; H1), and will experience fewer infections and nurse/ER visits (patients only, **secondary outcomes**; H2).

Specific Aim 3: Conduct moderator and mediator analyses. 3a: To examine the impact of identified moderators on intervention efficacy. Older age, female gender, and type of surgical diversion (i.e., non-neobladder) will moderate the relationship between the intervention and QOL (H3). **3b:** To examine the impact of identified

mediators on intervention efficacy. Higher levels of patient activation (i.e., self-care knowledge, self-efficacy) and lower levels of distress will mediate the intervention effect (H4).

Exploratory Aim 4: To examine the costs and potential savings associated with developing and implementing the RSBC intervention. Costs will be recorded in three categories: development, implementation, and maintenance of intervention. Potential savings will be recorded regarding emergency room care and unplanned visiting nurse home visits. Over time, the savings from the reduced ER/Nurse visits will surpass the costs of the intervention (H5) and the intervention will be cost effective (H6).

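### Aim 3a keeps only interactions with p < .05, so retained moderator effects will be overstated; separately, sections 2, 4 and 12 do not agree on which contrast tests H3

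*Combined protocol and SAP*

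**What the plan says.** Section 12 (Statistical Analysis) starts from the linear mixed model for QOL and says "we will add separate interaction terms of intervention group and age, gender, and diversion type". The selection rule follows: "Any interaction term that is statistically significant ($p < .05$) will stay in the final model". The same sentence gives the purpose; such a term "will stay in the final model so that the independent effects of the corresponding moderators will be determined". It then explains, with gender as the example, that a significant term means the variable moderates the causal effect of the intervention. It gives no multiplicity adjustment, no power for an interaction, and no coding for age. Section 12 also says "Analyses for patients and caregivers will be conducted separately".

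The moderators are described in three places:

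- Section 2 (Brief Summary): "RSBC will be significantly more successful among (a) older, (b) female participants, and (c) patients with a conduit diversion type".
- Section 4 (Specific Aim 3a): older age and female gender with no population named, and "type of surgical diversion (i.e., non-neobladder) will moderate the relationship between the intervention and QOL (H3".
- Section 12: the aim is to examine "whether the intervention works best for patients of older age, caregivers of female gender, and among patients with an ileal conduit diversion type".

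Section 7 admits patients with any of three diversions: ileal conduit, neobladder or Indiana pouch.

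**The concern.** There are two separate defects.

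**Selection.** H3 is fixed in advance, yet its terms are screened on significance. With the planned numbers, only a large observed interaction can reach p < .05, so the terms that stay carry estimates biased away from zero. A single unadjusted p-value is then read as showing that a moderator exists. A reader could conclude that the programme works mainly for one subgroup, and by an exaggerated amount, and direct implementation accordingly.

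**Definition.** Indiana-pouch patients belong to the favoured group under H3 (non-neobladder) but to the other group under section 12 (ileal conduit). Gender and age are unrestricted in sections 2 and 4 but tied to caregivers and patients respectively in section 12. Because the two populations are analysed separately, these are different tests in different samples. No section says which definition governs, so the choice could be made after the results are known.

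**Working it through.** **Inputs from the documents.** Final sample: 153 patients and 85 caregivers (section 8); 153 + 85 = 238, the stated total. Allocation is even between arms (section 11). Three interaction terms, p < .05 each, two populations (section 12). The plan states no error rate, power, effect size or SD for the interactions, so it has no figure of its own to reproduce on this point.

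**Assumptions.** Two-sided tests, residual SD 1, one outcome per person, a binary moderator with prevalence f of 25% or 50%, and true interactions of 0.3, 0.5 and 0.8 SD.

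**Step 1: at least one false moderator.** For k independent tests the chance is 1 − 0.95^k. The literal wording of section 12 names three moderator-population pairs: 1 − 0.95³ = 14.3%. Three terms in each of two populations: 1 − 0.95⁶ = 26.5%. These counts are for one QOL score and one time point.

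**Step 2: precision in patients (n = 153).** SE = √[4/(nf) + 4/(n(1 − f))].

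- f = 50%: √(4/76.5 + 4/76.5) = 0.323; smallest estimate that can be kept: 1.96 × 0.323 = 0.63 SD.
- f = 25%: √(4/38.25 + 4/114.75) = 0.373; smallest estimate that can be kept: 1.96 × 0.373 = 0.73 SD.

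**Step 3: mean estimate given retention.** With m = δ/SE and c = 1.96, the retention probability is P = Φ(m − c) + Φ(−m − c). The mean retained estimate is SE × {m + [φ(c − m) − φ(c + m)]/P}.

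| True interaction | f | Retained | Mean when retained | Ratio to truth |
|---|---|---|---|---|
| 0.3 SD | 50% | 15% | 0.78 SD | 2.6 |
| 0.3 SD | 25% | 13% | 0.88 SD | 2.9 |
| 0.5 SD | 50% | 34% | 0.85 SD | 1.7 |
| 0.5 SD | 25% | 27% | 0.96 SD | 1.9 |
| 0.8 SD | 50% | 70% | 0.96 SD | 1.2 |
| 0.8 SD | 25% | 57% | 1.06 SD | 1.3 |

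With no true interaction, a term that is kept averages 0.76 SD (f = 50%) to 0.87 SD (f = 25%) in absolute size. In caregivers (n = 85, f = 50%) the SE is 0.434 and the threshold 0.85 SD; a true 0.5 SD interaction is kept at a mean of 1.09 SD, 2.2 times the truth.

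**Step 4: estimates without the filter.** In simulation of 8,000 trials (n = 153, three moderators), the mean over all trials was 0.30 for a true 0.30 and 0.50 for a true 0.50. The bias comes from the selection, not from the model.

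**Step 5: sensitivity to the longitudinal design.** Assume four follow-ups averaged, correlation 0.5 throughout, and baseline adjustment. The variance factor is (1 + 3 × 0.5)/4 − 0.5² = 0.375, so at f = 50% the SE is 0.323 × √0.375 = 0.198. A true 0.3 SD interaction is then kept 33% of the time and overstated 1.7 times; 0.5 SD is overstated 1.2 times.

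**Step 6: the definitions side by side.**

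| | Section 2 | Section 4 (H3) | Section 12 |
|---|---|---|---|
| Diversion | conduit | non-neobladder | ileal conduit |
| Gender | female participants | female, population not named | female caregivers |
| Age | older participants | older, population not named | older patients |

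Suppose the true interaction is 0.5 SD for ileal conduit against both other types. The non-neobladder contrast then estimates 0.5 × conduit share/(conduit share + pouch share). With the advisory board's mix in section 7 (three conduit, one pouch, two neobladder; illustration only) that is 0.5 × 3/4 = 0.375. With an assumed 80% conduit and 2% pouch it is 0.5 × 80/82 = 0.49. The pouch share in the trial is not given.

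**The case against.** - **Selective reporting.** A reader might infer that non-significant interactions will go unreported. The documents do not say so: the rule fixes which terms stay in the model, not what is published. It also covers interaction terms only, not moderator main effects. What stands is that no report of the dropped terms is promised.
- **Error rate.** Each single test keeps its 5% level. What rises is the chance of at least one false finding and the size of the retained estimates.
- **Definitions.** Inconsistent definitions do not themselves inflate anything; they leave the contrast open. Section 12 enters diversion type, which could be a three-level factor, and adds gender without restriction a sentence after tying it to caregivers. Sections 2 and 4 agree on gender. So part of the conflict may lie in the directional hypothesis and not in the fitted term. The plan does not say, and the diversion groupings still differ.
- **Main effect.** A reader might infer that a retained interaction turns the primary effect into a reference-subgroup effect. That depends on coding and centring, which are not stated, and on the Aim 3a model replacing the Aim 2 model, which section 12 does not say. It merits a clarifying sentence, not a charge of error.
- **Size.** The ratios rest on assumed effects, SD and prevalence, and step 5 shows that they fall with repeated measures. The direction does not depend on these inputs; the size does.
- **Remedy.** A formal correction such as Holm is a choice for a non-primary aim and costs power: with Bonferroni over three terms, power in patients for a true 0.5 SD interaction falls from 27–34% to 15–20%. Separate models per moderator, or one particular diversion grouping, are likewise preferences. None is required here.

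**Conclusion.** The point holds in two separate parts.

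First, the p < .05 retention rule, with no multiplicity handling and with significance read as proof of moderation, yields overstated interactions among those retained. Under the stated single-time-point assumptions the overstatement in patients is about 2.6 to 3 times at 0.3 SD, 1.7 to 1.9 times at 0.5 SD and 1.2 to 1.3 times at 0.8 SD, and less with repeated measures and baseline adjustment. The chance of at least one false moderator is about 14% to 26%, depending on whether three or six independent tests are meant.

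Second, sections 2, 4 and 12 disagree on the diversion grouping and on the population for gender and age, so the test of H3 is not fixed. How much the diversion coding matters depends on the unstated share of Indiana pouches.

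The documents do not support the stronger readings that results will be selectively reported or that the primary effect estimate is compromised. As this is a secondary aim, the change should be made but does not threaten the primary analysis.

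**What to change.** 1. Delete the rule that only significant interaction terms stay in the final model.
2. Report every pre-specified interaction with its 95% CI and the subgroup effects, whatever its p-value. State how many interaction tests are made and interpret them with that number in mind; replace the statement that a significant term means moderation.
3. State that the overall intervention effect comes from the Aim 2 model without interactions.
4. Before data are seen, state one coding and one population for each moderator, identical in sections 2, 4 and 12: the diversion grouping, including where Indiana-pouch patients fall; whether gender and age are tested in patients, caregivers or both; and how age is coded.

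The cost is some wording and one more table. The downside is that fewer moderators will be claimed on a single p-value.
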